7.3 Exclusion Criteria

Subjects must be excluded from participating in this study if they meet any of the following Exclusion Criteria:

- 1) Subject, who, for any reason, is judged by the Investigator to be inappropriate for this study, including a subject who is unable to communicate or cooperate with the Investigator, who has/had a psychiatric illness, disability or social situation that may compromise the safety of the subject during the study or affect the ability of the subject to adhere to study procedures;
- 2) Subject has a medical history of clinically significant (as determined by the Investigator or the Sponsor) cardiac, renal, hepatic/biliary (e.g., sclerosing cholangitis), pulmonary, or other medical conditions or is not generally in good health.

Subjects with the history of immunologic, autoimmune or chronic inflammatory disorders (e.g., uveitis, rheumatoid arthritis, ankylosing spondylitis or spondyloarthritis, psoriasis) other than UC or autoimmune connective tissue diseases (e.g., systemic lupus erythematosus, systemic sclerosis) and are well controlled may be included into the trial after consultancy with medical monitor. Subjects with thyroid disorders, vitiligo, and alopecia are eligible for inclusion.

- 3) Subject's UC had failed to respond to:
 - a) Two or more biologic treatments with different mechanisms of action (e.g., infliximab, vedolizumab and golimumab), or
 - b) Three or more anti-TNF biologics, e.g., infliximab, adalimumab;
- 4) Subject requires prescription treatment for UC, except for the stable, oral treatment of UC as follows:
 - a) Aminosalicylates (5-ASA acid or mesalamine ≤ 4.8 g/day; sulfasalazine ≤ 3 g/day) for at least 14 days prior to the Screening visit; and/or
 - b) Glucocorticoids (≤ 20 mg/day prednisolone or the equivalent, or budesonide ≤ 9 mg/day) for at least 14 days prior to the Screening visit (or for 4 weeks if a course of corticosteroids had started at less than 8 weeks prior to Screening visit); and/or
 - c) Azathioprine up to 3 mg/kg/day or 6-mercaptopurine up to 1.5 mg/kg/day for a total treatment period of at least 12 weeks, including 4 weeks of stable treatment, prior to the Screening visit.
- 5) Subject has received any of the following prior treatments or treatments within the specified time:

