- 11) Subject has clinically significant cardiac disease (class II, III, or IV of the New York Heart Association [NYHA] classification) (The Criteria Committee of the NYHA Nomenclature and Criteria for Diagnosis of Diseases of the Heart and Great Vessels, 1994); unstable angina pectoris; myocardial infarction within 6 months or is post angioplasty or stenting within 6 months; uncontrolled hypertension; or clinically significant abnormality, such as cardiac arrhythmia, on a 12-lead electrocardiogram (ECG) at Screening;
- 12) Subject is pregnant or breastfeeding;
- 13) Subject has had major immunologic reaction (e.g., serum sickness, anaphylaxis, or anaphylactoid reaction);
- 14) Subject is Hepatitis B core antibody or surface antigen positive at Screening and/or Hepatitis C antibody positive with detectable RNA at Screening;
- 15) Subject has a history of human immunodeficiency virus (HIV) positivity, tests positive for HIV at Screening, or has congenital or acquired immunodeficiency;
- 16) Subject has or has had active TB, suspected extra-pulmonary TB, a history of incompletely treated TB, or latent TB or other latent infection. Subjects with latent TB (purified protein derivative [PPD] or interferon gamma release assay [IGRA]) may be included in the study if prophylactic therapy for latent TB is started at least 4 weeks prior to Screening. Subjects with a potentially untreated other infection (clinical findings) are to be excluded.

Note: Performing of both IGRA and PPD tests in the same subject should be avoided as screening procedures. Positivity of one of the tests cannot be voided by negativity of the other, i.e., subjects with positive PPD and negative IGRA test performed as a part of Screening will be considered TB positive and will be required to start prophylactic anti-TB therapy prior to infusion of investigational product according to local treatment standards. All safety laboratory tests may be repeated. Screening procedures may be extended by 2 weeks.

- 17) Subject has bacterial infections requiring treatment with oral or parenteral antibiotics (topical antibiotics are allowed), within 2 and 4 weeks, respectively, of the Screening period;
- 18) Subject has a history of systemic opportunistic infection or recurrent infections;

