9 STUDY PROCEDURES

It is important to maintain the visit structure as accurately as possible. Whenever an adjustment to this structure is necessary, the date of the adjusted visit should occur within the number of days (before or after) specified in the planned schedules for Screening, Induction Therapy, and Induction Therapy Post-treatment Follow-up Period (refer to Study Schedule of Events, Table 9-1) and for OLE/LTE Therapy and OLE/LTE Therapy Post-treatment Follow-up Period (refer to Study Schedule of Events, Table 9-2). The timing of any subsequent visits should be scheduled to maintain the visit structure relative to the first day that investigational product was administered.

Screening evaluations used to determine the subject's study eligibility must be completed within the Screening Period (Day -28 to Day -1) prior to starting treatment on Day 1 (Week 0) unless otherwise specified. Written informed consent must be obtained prior to any study-specific procedures. Results of all Screening evaluations must be reviewed by the Investigator or his/her designee to ensure that all eligibility criteria have been satisfied prior to randomization. For subjects who complete double-blind Induction Therapy and are eligible at Week 12 to receive treatment, additional criteria are required for enrollment in OLE/LTE Therapy (refer to Section 7.4 for the list of criteria).

All efficacy, PK, PD, immunogenicity, and safety measurements obtained during the course of the study are summarized in Table 9-1, Table 9-2, Table 10.4.1-1, and Table 10.4.1-2.

Table 9-1 Study Schedule of Events - Screening, Induction Therapy, and Follow-up Period

Procedure	Screening Day -28 to Day -1	Treatment Period - Double-blind Induction Therapy: Weeks 0 to 12 (Last dose at Week 10) ^a (All Randomized Subjects)							Induction Therapy Post-treatment Follow-up Period for Subjects Not Enrolling in OLE Therapy		
		Baseline						End-of- Induction Therapy	Follow- up 1	Follow- up 2	Follow- up 3
		Week 0 Day 1	Week 2 ± 2 days	Week 4 ± 4 days	Week 6 ± 4 days	Week 8 ± 4 days	Week 10 ± 4 days	End-of- Treatment Week 12 ± 4 days	Week 16 ± 7 days	Week 20 ± 7 days	End-of- Study Week 26 ± 7 days
Written Informed Consent	X										
Inclusion/Exclusion Criteria	X	X									
Medical, Diet & Surgical History/ Demographics	X										
Physical Examination ^b	X	X						X			
Brief Physical Examination ^c			X	X	X	X	X		X	X	X
Vital Signs ^d	X	X	X	X	X	X	X	X	X	X	X
Body Weight	X	X	X	X	X	X	X	X	X	X	X

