9.1 Screening Period (Day –28 to Day –1)

At the Screening visit, the Investigator will review the ICF with each subject to ensure that the subject understands the study and the study procedures. The subject will read, sign, and date the ICF and other locally applicable documents. Screening evaluations used to determine the subject's study eligibility must be completed within the Screening Period (Day –28 to Day –1) prior to starting treatment on Day 1 (Week 0), and include a baseline sigmoidoscopy with biopsy being completed within 7 to 28 days prior to Day 1. For subjects who are rescreened, the original screening sigmoidoscopy can be used to satisfy the entry criteria if obtained within 42 days prior to the first dose. All sigmoidoscopy procedures will be performed using a flexible sigmoidoscope. Biopsies will be collected during the sigmoidoscopy procedure and tissue samples will be examined at a central laboratory. Immunohistochemical staining will be performed on all biopsy samples (refer to Section 10.4.1). Sigmoidoscopy scores will be determined by a central reader. The sigmoidoscopy results from the central reader are required before a subject is randomized in the study.

Subjects will be instructed on how to appropriately complete a daily diary to document symptoms of UC including stool frequency, rectal bleeding, abdominal discomfort, and general sense of well-being. Symptoms of UC must be recorded throughout the Screening Period. Diary entries will be reviewed by site personnel at all visits.

All subjects must satisfy all the Inclusion Criteria and none of the Exclusion Criteria listed in Sections 7.2 and 7.3, respectively.

A subject who was considered a Screen failure and not dosed with the investigational product is permitted to be re-screened once due to failure to meet the Inclusion/Exclusion Criteria, whereas subjects with other reasons for lack of randomization may be re-screened twice.

The following additional assessments will be performed during the Screening Period (Day –28 to Day –1) (refer to Table 9-1 for the schedule of study events at Screening):

- Main diagnosis - moderately active UC, severity of UC, duration of UC (sigmoidoscopy scores will be determined by a central reader);
- Demographics - age at Screening, sex, race, and ethnicity identifications;

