- Medical and Surgical History - including concurrent illnesses; chest x-ray if needed (within previous 3 months) results, vaccinations (within previous 6 months), previous surgery for UC or other major or abdominal surgery, and anticipated requirement for surgery for UC or other major surgery;
- Childbearing potential;
- Complete physical examination (Section 10.6.4);

- Vital Signs (systolic and diastolic blood pressure, radial pulse, and respiration rate) and body temperature (oral) (Section 10.6.2);
- Body weight and height (Section 10.6.4);
- 12-lead ECG (Section 10.6.3);
- Previous treatment with corticosteroids, immunosuppressive medications or TNF antagonist therapy, any prior biologic treatment (e.g., infliximab, adalimumab, or golimumab), and prior investigational products or therapies (Section 8.5);
- Prior and concurrent prescriptions and non-prescription medications, including any other UC treatments such as probiotics and other over-the-counter medications and supplements. Stable doses of aminosalicylates, oral glucocorticoids, azathioprine, and 6-mercaptopurine are permitted as described in Section 8.5 (refer to Section 8.5.1 for prohibited medications);
- Tobacco use, alcohol use, active marijuana (medicinal or recreational) use, illicit substance use;
- Allergies/hypersensitivities;
- Diet special for UC;
- Pre-treatment AEs (Section 10.6.5);
- Clinical Laboratory Evaluations (Table 9-1; refer to Section 10.6.1 for list of tests): Blood samples will be drawn at Screening for serum chemistry, hematology, coagulation profile, serum pregnancy, hepatitis B and C, and HIV testing; TB screening will be performed using a PPD skin test or IGRA; urine samples will be collected for analysis and urine drug screen; and fecal samples will be collected (before the start of the preparations required for the sigmoidoscopy or as specified in the stool collection instruction section of the laboratory manual) for analysis, i.e., cultures for enteric pathogens, ova and parasite evaluation, and *Clostridium difficile* assay.
- Delayed-type hypersensitivity skin test with the *Candida albicans* antigen - at all investigative sites in the US and in other selected countries (Section 10.4.1). The skin testing site will be read within 48 to 72 hours following intradermal injection of the antigen. The largest diameter of induration will be measured in mm and recorded.

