Hepatitis B and C, and HIV testing	hepatitis B surface antigen or hepatitis B core antibody hepatitis C antibody (If positive, do reflex to RNA by RT-PCR testing) HIV-1 antibodies, HIV-1 antigen, HIV-2 antibody		

Table 10.6.1-1 Clinical Laboratory Assessments

Tuberculosis Screening using PPD Skin Test (by investigative site) and/or IGRA (clinical laboratory) (See details in Section 7.3, Exclusion Criterion 16)
	
Standard PPD skin test or IGRA (but not both) to be performed at Screening at investigative site. If positive (i.e., PPD measures > 5 mm induration), follow up after Screening is required. An IGRA is to be performed at Screening if a subject has a history of positive PPD.
 
Note: Performing of both IGRA and PPD tests in the same subject should be avoided as Screening procedures. Positivity of one of the tests cannot be voided by negativity of the other, i.e., subjects with positive PPD and negative IGRA test performed as a part of Screening will be considered TB positive and will be required to start prophylactic anti-TB therapy prior to infusion of investigational product according to local treatment standards. All safety laboratory tests may be repeated. Screening procedures may be extended by 2 weeks.

Delayed-Type Hypersensitivity Skin Test
	
At investigative sites in the US and other identified countries, the skin tests are to be performed at Screening and Week 10. The skin testing site will be read within 48 to 72 hours following intradermal injection of the Candida albicans antigen. The largest diameter of induration will be measured in mm and collected.

Fecal Sample Analysis
	
Stool cultures to identify enteric pathogens, ova and parasite evaluations, and Clostridium difficile assays are to be performed at Screening, Week 12, and Week 52. Refer to PD assessments for fecal calprotectin measurements at Baseline (Week 0) and Weeks 2, 12, and 52.

a: A subject will be excluded from the study if a specific serum chemistry or hematology value at Screening is outside of the acceptable range as defined in Section 7.3, Exclusion Criteria.

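### For latent TB first detected during Screening, Exclusion 16 and its Note give conflicting start times for prophylaxis: at least 4 weeks before Screening, or merely before infusion

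*Protocol*

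**What the plan says.** Exclusion 16 appears in the Synopsis and in Protocol Section 7.3. It excludes active TB, incompletely treated TB and latent TB, with one exception: subjects with latent TB "may be included in the study if prophylactic therapy for latent TB is started at least 4 weeks prior to Screening".

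A Note follows. It advises against doing both a PPD and an IGRA, and says that a negative result on one cannot cancel a positive on the other. It gives the example of a positive PPD with a negative IGRA, both done as part of Screening. Such subjects count as TB positive and "will be required to start prophylactic anti-TB therapy prior to infusion of investigational product according to local treatment standards". The Note then allows safety laboratory tests to be repeated and adds that "Screening procedures may be extended by 2 weeks".

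The TB row of Table 10.6.1-1 (Section 10.6.1) repeats the Note. It does not repeat the 4-week rule, which it reaches only through a pointer: "See details in Section 7.3, Exclusion Criterion 16".

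Section 9.1 makes the test part of Screening: "TB screening will be performed using a PPD skin test or IGRA".

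Three general rules govern entry:
- Section 7.3: "Subjects must be excluded from participating in this study if they meet any of the following Exclusion Criteria".
- Section 9: Screening results are reviewed "to ensure that all eligibility criteria have been satisfied prior to randomization".
- Section 9.1: "All subjects must satisfy all the Inclusion Criteria and none of the Exclusion Criteria".

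Section 9.2 repeats the eligibility review at Baseline. Section 7.1 allows one re-screen after an eligibility failure.

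**The concern.** The two timing rules are tied to different events. The criterion counts back from Screening; the Note counts only to the first infusion. For a subject whose latent TB is unknown until the Screening test, the first rule is already missed when the result arrives, while the second can still be met. The Note tells the site what to do next, and that instruction reads as a route to dosing within the same Screening.

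A safety requirement is at stake. The product targets OX40, which Section 4.3.1 describes as sustaining T-cell proliferation, survival and memory formation. Section 4.2 lists TB among the serious infections reported with TNF-alpha blockers. A site acting in good faith on the Note could infuse a latent-TB subject after much less prophylaxis than the criterion demands, while another site would screen-fail the same subject.

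**Working it through.** The plan gives no figure to reproduce. The check is on dates.

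**Inputs**
- Criterion: prophylaxis starts at least 28 days before Screening (Section 7.3, Exclusion 16).
- Note: prophylaxis starts before infusion; no minimum beyond local standards (same place).
- Screening: Day -28 to Day -1, so up to 28 days (Sections 9 and 9.1). There is no Day 0 (SAP Section 4.1), so Day -28 is 28 days before Day 1.
- Extension: 14 days (Note), giving 28 + 14 = 42 days at most.

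Let S be the start of Screening, P the start of prophylaxis, and L the number of days from S to the first infusion on Day 1.

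**Known latent TB, already treated.** The criterion needs P ≤ S - 28. Any such P also precedes infusion, so both texts are met.

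**Newly detected at Screening.** The test is a Screening procedure, so a start prompted by it has P ≥ S. This inequality comes from the scenario, not from the Note's wording. The criterion still needs P ≤ S - 28. No date meets both, and the gap is at least 28 days.

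| Screening | Criterion: P no later than | Newly detected: P no earlier than |
|---|---|---|
| 28 days, S = Day -28 | Day -56 | Day -28 |
| 42 days, S = Day -42 | Day -70 | Day -42 |

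Extending Screening adds time after S; it cannot place P before S.

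**Prophylaxis before first infusion.** The criterion guarantees at least 28 + L days: 56 for L = 28, 70 for L = 42. A start prompted by the Screening test gives at most L days: 28 or 42. The shortfall is at least 28 days, and the protocol itself sets no floor under the Note.

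**Could the 4 weeks simply mean before dosing?** Exclusion 5 counts its washouts from randomization at the Baseline visit, while Exclusion 16 says Screening, so the wording does not support treating the two anchors as one. If the count did run to first infusion, prophylaxis would have to start by Day -28. A 42-day Screening would leave 42 - 28 = 14 days for the test and its result; a 28-day Screening would leave essentially none.

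**The case against.** The best defence is that the sentences are not logically inconsistent. Anyone who meets the criterion also meets the Note, so the Note can be read as a necessary condition only. It never says that the subject may then be randomized; permission to enter appears only in the criterion. The rules in Sections 7.3, 9, 9.1 and 9.2 all require that no exclusion is met, and Section 6.3 adds medical monitoring of adherence to eligibility criteria. Starting prophylaxis, waiting 4 weeks and using the one re-screen would satisfy both texts. The worked example needs both tests, which the Note discourages and Table 10.6.1-1 limits to one. The table also asks for follow-up after Screening when the PPD is positive, which counts somewhat against going straight to dosing.

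Much of this stands. It narrows the problem to newly detected positives, explicitly only the discordant case, and makes wrongful dosing less likely. It does not remove the conflict. An instruction to start prophylaxis before infusion has little purpose for a subject who is already excluded. The Note mentions neither screen failure nor re-screening, and the table repeats it without the 4-week rule.

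A reader might go further and take the 2-week extension as a built-in prophylaxis window. The documents do not support that: the sentence follows the one on repeating laboratory tests and is not tied to prophylaxis.

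**Conclusion.** The point holds for a subject whose latent TB is first detected by a test done during Screening: the criterion and its Note cannot both lead to entry in that Screening, and no text says which governs. The Note's wording covers the PPD-positive, IGRA-negative case; extending it to any new positive is a reading of its evident purpose. Subjects treated for at least 4 weeks before Screening are unaffected.

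The gap is at least 28 days of prophylaxis before first infusion, assuming that prophylaxis is prompted by the Screening test. The number of such subjects cannot be derived. A reader might infer that the protocol authorises dosing of latent TB with prophylaxis barely begun, or that this happened. Neither follows: the eligibility checks stand against it, and the documents contain no enrolment data.

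Severity is minor to moderate. It is a safety and eligibility ambiguity; sample size and analysis are unaffected.

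**What to change.** In the Synopsis, Section 7.3 and Table 10.6.1-1, replace the instruction tied to infusion with: *A subject newly found TB positive at Screening is a screen failure under Exclusion 16 and may be re-screened once (Section 7.1), after at least 4 weeks of prophylaxis given to local treatment standards.* Keep the sentence that a negative result on one test cannot void a positive on the other.

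If the sponsor meant 4 weeks before dosing, amend both the criterion and the Note to require at least 4 weeks before the first infusion. The extended Screening can accommodate this and no re-screen is used. The sigmoidoscopy must then be timed within the usual 7 to 28 days before Day 1, because the 42-day allowance in Section 9.1 is only for re-screened subjects.

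The edit is one sentence in three places (criterion and Note under the alternative). Under the first option the costs are at least 28 days' delay or the loss of a few subjects, use of the single eligibility re-screen, and a repeat sigmoidoscopy for some. If the first sigmoidoscopy was done k days before prophylaxis began, and re-screening starts as soon as 28 days are complete, 42 - 28 - k = 14 - k days remain to reach the first dose: 14 at k = 0, 7 at k = 7, none at k = 14. Deferring the sigmoidoscopy until the TB result is known eases this.

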7.4 Additional Criteria to Enroll in Open-label Extension Therapy

Prior to receiving investigational product (one infusion every 4 weeks) in the OLE, subjects must meet the following criteria:

- 1) Subjects must have completed double-blind Induction Therapy, i.e., at least five of six double-blind treatments, or the subject is already in the double-blind LTE and not beyond Week 28 with a clinical worsening or a flare of disease as defined by the Investigator;
- 2) Subjects must have evaluable total Mayo Clinic scores at Baseline and Week 12;
- 3) Subjects must have been compliant with the protocol (including concomitant medication restrictions); and
- 4) Subjects may have no clinically significant additional risks, as determined by the Investigator or the Sponsor, of treatment with KHK4083.

7.5 Withdrawal and Termination Criteria

In accordance with the Declaration of Helsinki, each subject is free to withdraw from the study at any time. Investigator(s) also have the right to withdraw subjects from the study in the event of illness, AEs, or other reasons concerning the health or well-being of the subject, or in the case of lack of compliance with the protocol.

7.5.1 Subject Withdrawal

During the conduct of the study, the Sponsor will review the safety data for trends and signals that would indicate the need for withdrawal of a subject. The Investigator may withdraw a subject from the study for any of the following reasons:

- For any of the specific criteria listed in Section 7.5.3;
- Pregnancy;
- For any reason judged by the Investigator to be inappropriate to continue in the study, including a subject who is unable to communicate or cooperate with the Investigator, who has/had a psychiatric illness, disability or social situation that may compromise the safety of the subject during the study or affect the ability of the subject to adhere to study procedures;
- The study is terminated by the Sponsor;
- Any therapy-related event that is deemed life-threatening, regardless of intensity;
- Protocol noncompliance;
- Withdrawal of consent.

Should a subject decide to withdraw after administration of the investigational product (KHK4083 or placebo), or should the Investigator(s) decide to withdraw the subject, all efforts will be made to complete and report the observations up to the time of withdrawal as thoroughly as possible. A complete final evaluation at the time of the subject's withdrawal should be completed and an explanation given as to why the subject is withdrawing or being withdrawn from the study.

The reason for withdrawal must be collected. If the reason for withdrawal is a clinical AE, whether considered to be related to investigational product or not, the AE must be monitored until the return to the subject's baseline condition or until clinically satisfactory resolution is achieved (e.g., Grade 1 or stable). The clinical course of the AE will be followed according to accepted standards of care or medical practice, even after the end of the period of observation until a satisfactory explanation is found or the Investigator considers it medically justifiable to terminate follow up (e.g., event returned to subject's baseline, Grade 1, or stable).

